### Background:

Heart failure (HF) has reached endemic proportions effecting over 5.4 million people worldwide and its burden is projected to exponentially grow in the next decade [1]. HF is a progressive syndrome and despite improvements in medical therapy, most patients will develop advanced HF overtime. With implementation of the current generation of durable CF pumps, the 2-year survival for patients with chronic advanced HF has improved to nearly 70% [2]. For patients in acute cardiogenic shock, CF pumps such as veno-arterial extracorporeal membrane oxygenation (VA-ECMO) or Impella have become a major mode of temporary cardiac support until recovery, durable CF pump implantation or transplantation. Utilization of VA-ECMO has grown by over three-fold during the prior decade with survival outcomes of 40-50% for otherwise moribund patients; however, these outcomes have remained stagnant [3]. Despite these remarkable improvements in survival with durable CF pumps and the clear lifesaving effects of Impella and VA-ECMO, serious adverse hematological events such as bleeding and thrombosis create substantial morbidity and mortality and remain major barriers for further expansion of this technology. In particular, thrombosis is a devastating adverse event during CF pump support as it can lead to stroke, device stoppage, and hemodynamic collapse. Although the annual incidence of pump thrombosis has been reported to range from 8 to nearly 30% [4, 5] the pathobiological

mechanisms of thrombus formation during CF pump support with ongoing anticoagulation remain elusive [4, 6].

[figure not shown]

Figure 1: A. Pathway of free hemoglobin induced thrombus formation during diseases of intravascular hemolysis such as sickle cell anemia. Free hemoglobin released from red blood cell lysis depletes nitric oxide (NO) by converting it to nitrate. Free hemoglobin binds ultra large (UL) and high molecular weight (HMW) multimers of vWF to prevent their proteolysis by ADAMTS 13. Reduced NO and more UL multimers create a pro-thrombotic state by increasing platelet activation and aggregation leading to thrombus formation. LDH is released from red blood cell lysis and serves as a biomarker for hemolysis.

### Hemolysis and thrombotic events:

The incidence of hemolytic events during durable CF pump support is estimated to be 15-35% and may affect as many as 1 in every 3-4 patients [7-9]. We have previously shown that a majority of pump thrombosis events are from non-mechanical etiologies and occur more frequently with pre-existing pro-thrombotic conditions. Several investigations show elevated LDH levels in patients many weeks before pump thrombosis is apparent clinically [4, 7-9]. After durable CF pump implantation, LDH levels are clinically screened biweekly and a rise to >700 U/L, prompts further exploration of mechanical and non-mechanical etiologies. Although conventional wisdom in the MCS field has been that hemolysis is a result of

thrombus obstructing blood flow, such observations have led to speculation that hemolysis may precede and indeed trigger thrombus formation.

***Pathophysiology of hemolysis induced thrombus formation:*** It is conceivable that low-grade hemolysis occurring in CF pumps due to transient turbulence, high shear stress, increased afterload and/or heat related fibrin deposition could be the inciting events for thrombus formation. Specifically, following the release of free hemoglobin with its potent inhibitory effects on nitric oxide (NO) bioavailability and stabilization of pro-thrombotic ultra large (UL) and high molecular weight (HMW) vWF multimers, an increase in platelet activation and aggregation may occur (**Figure 1**). The preceding sequence of events triggered by free hemoglobin has been well described in diseases of ongoing hemolysis such as sickle cell anemia (SCA) and paroxysmal nocturnal hemoglobinuria (PNH) [10, 11]. Furthermore, recent *in vitro* studies reveal that exposure of purified platelets to red blood cell hemolysate or extracellular free hemoglobin increases platelet activation and aggregation in a dose dependent manner. [name] and colleagues (collaborators on this proposal) showed through platelet aggregometry that increasing concentrations of plasma free hemoglobin and RBC hemolysate increased PA/A (**Figure 2**) [12].

[figure not shown]

Figure 2: Platelet aggregation induced by RBC-hemolysate (blue bars) and maximal platelet aggregation mediated by additional adenosine diphosphate (orange bars). B. Scanning electron microscope of platelet aggregation after exposure to RBC hemolysate. (images courtesy of [name]).

#### ***Inhibition of NO and increased platelet activation by extracellular free hemoglobin:***

NO is produced by endothelial as well as circulating blood cells and its hematologic functions include inhibition of platelet activation, aggregation, and release of procoagulant proteins. Free hemoglobin directly limits NO bioavailability by oxidizing it to nitrate [13]. NO represses platelet activation and when its bioavailability is reduced during ongoing hemolysis, the propensity of platelet activation and aggregation is increased, creating a nidus for thrombus formation [10]. NO also activates guanylate cyclase producing cGMP and activating G kinase. G kinase in turn

phosphorylates the thromboxane (TXA2) receptor on platelet membranes which disrupts coupling of this receptor to its GTP binding protein Gq to inhibit activation of effector phospholipase C, thereby preventing Ca2+ mobilization and platelet activation [14]. Moreover, inhaled NO in patients with Acute Respiratory Distress Syndrome has been shown to inhibit platelet aggregation by reduced binding to fibrinogen [15, 16]. Consistent with this model, sildenafil, which potentiates NO signaling by inhibiting phosphodiesterase-5 (PDE-5) to prevent breakdown of cGMP, *decreases* platelet activation in patients with SCA [10, 17]. Moreover, inhibition of PDE-5 with sildenafil is known to improve endothelial dysfunction [18] which may further reduce platelet activation and thrombotic events such as stroke.

#### ***Possible role of Ultra Large (UL) and High Molecular Weight (HMW) multimers of von Willebrand Factor (vWF) in creating a prothrombotic state:***

vWF is a very large protein (>20,000 kDa) consisting of 250 kDa subunits that polymerize in the Weibel Palade bodies within endothelial cells. It is constitutively released and can be broken down in the circulation to smaller multimers. For hemostasis, UL multimers activate and aggregate platelets to initiate thrombus formation, while HMW multimers have a more

homeostatic role. Excessive UL and HMW multimers are associated with thrombosis in conditions such as thrombotic microangiopathies [18] and sepsis-induced disseminated intravascular coagulation [19]. Conversely, loss of vWF HMW multimers leads to a bleeding diathesis as evident in congenital and acquired vWF deficiency disorders [20].

The breakdown of UL and HMW multimers is controlled by ADAMTS 13. Under conditions of supra-physiologic shear stress, such as during CF pump support, the tensile force on VWF is increased by the square of the multimer length, thereby providing a mechanism for elongation and exposure of its cleavage site for ADAMTS 13 [21]. The resultant proteolysis of UL and HMW multimers leads to a type 2A VWF deficiency which is noted during CF pump support [22, 23]. Persistent hemolysis, which occurs during SCA and PNH, creates pro-thrombotic conditions by preventing breakdown of UL and HMW multimers [10, 11]. During hemolysis, free hemoglobin and its metabolic product, unconjugated bilirubin, can inhibit the normal cleavage of UL and HMW multimers by binding to them and preventing proteolysis by ADAMTS 13 [11, 24]. In patients with SCA, up to 14% of the total plasma VWF (4 fold higher than normal) is bound to extracellular hemoglobin [10, 11]. Additionally, hemoglobin-bound multimers are more adhesive to platelets and more hemostatic when assessed ex-vivo by the ristocetin co-factor and collagen binding assays [11]. Furthermore, recent investigations with in-vitro high shear stress models that emulate CF pumps show that free hemoglobin increases VWF-mediated platelet adhesion [25]. Taken together, extracellular free hemoglobin released during hemolysis can bind to UL and HMW multimers to create a substantially pro-thrombotic substrate. Whether the observed hemolysis induced pro-thrombotic milieu during CF pump is related to reduced breakdown of UL and HWM multimers remains underexplored.

## **Research Protocol and Study Procedures**

### **Aim 1: To evaluate LLH-related PA/A during CF MCS.**

**Design:** In a cross-sectional format, we will recruit patients on chronic and acute CF MCS devices. Device-specific comparisons will be made to assess PA/A between those with and without LLH. In secondary analyses, we will also examine association of LLH with potential mediators of PA/A including activated GP IIb/IIIa receptor, p-selectin, platelet cGMP, vWF activity, vWF UL/HMW multimers and ADAMTS13 activity.

**Population:** Patients  $\geq 18$  years old on durable (HM2 and HM3) and acute (VA ECMO and Impella) CF MCS devices will be approached for participation. We will only approach HM3 patients that are commercially implanted and not enrolled in an ongoing clinical trial. Patients receiving sildenafil or nitrates for clinical indications will be excluded. Plasma Free Hemoglobin (PFHb) and Lactate Dehydrogenase (LDH) levels used to categorize patients as LLH (PFHb 10-20 mg/dL and LDH 400-700 U/L on three consecutive clinical measurements within a 14-day period to assure steady state) or no LLH (PFHb  $< 10$  mg/dL and LDH  $< 400$  U/L) are clinically measured daily in inpatients and every 2 weeks in outpatients at our institution.

Adult patients requiring acute CF pump support with veno-arterial (VA) ECMO or the Impella device for cardiogenic shock with an anticipated support time of at least 48 hours will be approached for participation in this study. The capacity to give informed consent will be evaluated by the study team. Patient's capacity will be assessed through the MacArthur

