## Competence Assessment.

**Protocol:** After acquiring informed consent from the patient, 8 am fasting blood (7 tubes, 3 ml per tube = 21 ml total, **table 1**) will be collected to measure PA/A. Newly implanted patients with durable devices will have blood samples drawn on the day of discharge and outpatients will be asked to come into the heart failure clinic for a scheduled research visit. In-patients with acute CF pumps will be screened and enrolled 48 hours after device implantation. For enrolled in-patients with ongoing LLH, we will also draw serial blood tests (3 tubes, 3 ml per tube = 9mL) daily for up to three days to monitor PA/A studies, to assess ongoing effects of LLH on platelets.

Table 1: Hematologic studies for Aim 1	Durable CF Pump HM2 (n=50) and HM3 (n=75)		Acute CF Pump VA ECMO (n=45) and Impella (n=45)	
	LLH (HM2 n=15; HM3 n=15)	no LLH (HM2 n=35; HM3 n=60)	LLH (n=15 per device)	no LLH (n=30 per device)
PA/A studies (3 lightblue top tubes)				
-Aggregometry	x	x	x	x
-Flow Cytometry: P Selectin and GP 2b3a in platelet rich plasma				
Platelet cGMP measurement (1 blue top tube)	x	x	x	x
von Willebrand Factor electrophoresis and antigen/activity (2 lightblue top tubes)	x	x	x	x
ADAMTS-13 activity (1 lightblue top tubes)	x	x	x	x

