polyclonal rabbit antihuman antibody to vWF from Dako Inc. will be used to identify vWF multimers' bands which will be further quantified by densitometry. VWF activity will be measured from plasma (3ml) as the ratio of vWF collagen binding activity (measures binding of vWF to collagen as a function of the quantity of HMW multimers) to vWF antigen.

4. ADAMTS13 testing: Whole-blood samples (3 ml) will be centrifuged, and plasma will be removed. After repeat plasma centrifugation to remove platelet contamination, plasma specimens will be assessed for ADAMTS13 activity. This will be measured by a fluorescence resonance energy transfer (FRET)-based assay using a 73 amino-acid peptide (FRETS-VWF73) of von Willebrand factor (vWF) as a substrate [29].

*\*Plasma specimens for platelet cGMP, vWF and ADAMTS 13 activity studies will be frozen at -80°C and stored for analysis every week in batches during study period.*

5. LDH and plasma free hemoglobin are clinically measured daily on all inpatients and every 2 weeks in all outpatients with CF pumps by our institution's coagulation laboratory. As stated in the career and training plan, the candidate will be trained in the [name], [name], and [name] labs to become adept in platelet aggregometry, flow cytometry, the PAS assay and vWF and ADAMTS 13 activity studies. Then the proposed studies will be performed by the candidate at the home institution in [name] laboratory. In addition, a laboratory technician will be employed and trained to further assist with platelet aggregometry, flow cytometry (p-selection, GPIIb/IIIa receptor), platelet cGMP ELISA assays, VWF and ADAMTS13 activity studies.

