**Statistical analysis, sample size calculations and timeline:** The primary measure for PA/A is ADP-induced AUC assessed by platelet aggregometry. ADP-induced AUC will be compared between the LLH and no LLH groups with an unpaired Student's t test. The null hypothesis is that there will be no difference in the PA/A between groups. A prior in-vitro study suggested that LLH increases PA/A by at least 30% as measured by aggregometry from  $20\pm 5$  to  $26\pm 4$  AU [12]. If this is the true population effect of LLH on PA/A in patients with CF pumps, with a minimum of 15 patients in each group per device we would achieve **90% power** to detect a significant difference in means with a two-sided alpha of 0.05. Since there will be fewer patients with LLH, we will recruit for both groups until we have enrolled 15 patients in the LLH group for each device. As device specific comparisons will be made, for durable CF pumps we estimate that we will have to screen 80 HM2 and 115 HM3 patients. We estimate that 35% of these patients will be excluded due to being on sildenafil, nitrates, active infection or withholding consent. This will leave 50 HM2 and 75 HM3 patients available for analysis. From historical data [30], we expect that approximately 30% of HM2 (n=15) patients and 20% of HM3 (n=15) will have LLH and the remainder will be in the no LLH group (35 HM2, 60 HM3). For acute CF pump support, we estimate that 90 VA ECMO and 90 Impella patients will need to be screened and after 50% exclusion, 45 VA ECMO and 45 Impella will be enrolled and available for analysis. Based on our preliminary data (**Figure 3C**) for VA ECMO and prior reports in Impella [31], we expect that at least 35% of patients for each acute CF pump (n=15 per device) will have LLH and the remainder will be in the no LLH group (n=30). At our institution there are 5 durable CF pumps implants (3 HM3 and HM2) and 6 acute support CF pumps (3 VA ECMO and 3 Impella) implanted every month. In addition, there are currently 125 stable outpatients with durable CF pumps (95 HM2 and 30 HM3) available for screening. Therefore, we estimate it would take 32 months to enroll and analyze the calculated number of patients for all devices (see timeline). For each device specific comparison, we will examine the confounding effects of age, sex, body mass index, race/ethnicity (such variables are known to effect

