thrombosis during CF MCS) by comparing them between LLH and no LLH groups. If significant differences are found then adjusted multivariable models will be used to assess the independent association of LLH and PA/A. We will also assess if there are device differences by conducting a 1-way ANOVA test of the difference PA/A between LLH and no LLH amongst all 4 device groups and post-hoc comparisons if any significant difference is observed. Results from devices that do not show heterogeneity will be pooled to assess the association across device type. Similar to the device specific analysis noted above, confounders will also be examined, and if appropriate, adjusted for in this pooled sample. Lastly, we will compare for each device and in any pooled analysis, the association of LLH with potential mediators of PA/A including p-selectin, activated GP IIb/IIIa receptor, cGMP, vWF activity, UL/HMW multimers, ADAMTS 13 activity by unpaired Student's t tests.

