**Plan for recruitment, retention, timeline and check points:** Patients on CF MCS are tracked closely in a centralized electronic medical registry kept by the HF group, which we will continue to leverage as a resource to identify patients. Currently, 52 outpatients identified through our CF MCS patient registry on durable devices with LLH are available for screening and at the current implant rate of 5 durable devices per month, 1 additional patient with LLH becomes available every month. With an estimated 35% ineligibility or withholding consent, 95 patients with LLH will need to be screened to enroll 62 patients. With an additional 25% drop-out rate after enrollment, this will leave 46 patients (23 per group) who will complete the study protocol. Since 52 outpatients with CF pumps and LLH are currently available (which is steady state for our program based on prior 3 years) and taking into account 35% ineligibility or unwillingness to participate at screening, we estimate that 34 patients can be immediately enrolled to get a head start. At the current availability of 1 new LLH patients per month, it will take an additional 42 months to screen and enroll the remaining patients. We will conduct checkpoints every 6 months examining if the anticipated enrollment (table 2) is being achieved. If enrollment is not met by 2 consecutive check points, we may increase recruitment an additional 6-12 months.

**Anticipated results and experimental problems:** We expect that enhancement of NO signaling with Sildenafil in patients with low level hemolysis will lead to a reduction in PA/A. If changes in PA/A are not observed, then exogenous PA/A will be assessed with platelet poor plasma. If PA/A is not affected, then follow-up experiments will have to be designed to identify the LDH and plasma free hemoglobin threshold value at which lower-level hemolysis increases PA/A.

Alternatively, if the expected reduction in PA/A is not observed with sildenafil we may try other pharmacological agents that also enhance NO signaling such as nitrates.

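### Aim 1's rule for an LLH case (three values within 14 days) cannot be met on the 2-weekly outpatient schedule, so HM2 and HM3 outpatients have no workable written case rule; separately, Aim 2's free-hemoglobin unit and connector are unclear

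*Combined protocol and SAP*

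**What the plan says.** **Aim 1 case rule.** The Population paragraph of Aim 1 defines a case as "LLH (PFHb 10-20 mg/dL and LDH 400-700 U/L on three consecutive clinical measurements within a 14-day period to assure steady state". The comparison group needs PFHb below 10 mg/dL and LDH below 400 U/L, with no number of measurements and no window stated.

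**Measurement schedule.** The same sentence says the two laboratory values "are clinically measured daily in inpatients and every 2 weeks in outpatients at our institution". Item 5 of the Aim 1 Study Procedures repeats it: "LDH and plasma free hemoglobin are clinically measured daily on all inpatients and every 2 weeks in all outpatients with CF pumps".

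**Sources of durable-pump patients.** Under the Aim 1 Protocol paragraph, "Newly implanted patients with durable devices will have blood samples drawn on the day of discharge", and outpatients attend a scheduled research visit. The Aim 1 statistical section adds that "there are currently 125 stable outpatients with durable CF pumps (95 HM2 and 30 HM3) available for screening".

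**Confounders in Aim 1.** The statistical section states that "we will examine the confounding effects of age, sex, body mass index, race/ethnicity", by comparing them between groups. It continues: "If significant differences are found then adjusted multivariable models will be used to assess the independent association of LLH and PA/A". Inpatient or outpatient status and time since implant are not listed. The Aim 2 secondary analysis does adjust for duration of implant.

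**Aim 2 definition.** The Aim 2 inclusion criteria define LLH by LDH of at least 240 U/L, plasma free hemoglobin of at least 10 g/dL and haptoglobin of at most 100 mg/dL. The three criteria are separated by commas only.

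**The concern.** The case rule and the outpatient schedule contradict each other within one sentence, and the mismatch is one-sided: it blocks outpatients from being cases but not from being controls. It affects two of the four device comparisons. There are two ways to run the plan as written.

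- **Literal.** Outpatients on the routine schedule are only ever controls. Durable-pump cases come essentially from new implants sampled at discharge. New implants without LLH are sampled then too, so the separation by setting is partial. A platelet-function difference due to recovery or setting could appear as an LLH effect or, with the opposite sign, mask one.
- **Relaxed.** Staff classify outpatients by a rule that is not written. Steady state then means one thing for inpatients and another for outpatients, and a reader cannot reconstruct the exposure.

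For Aim 2, the stake is narrower: which rule admitted the enrolled participants, 20 of whom had completed according to the addendum.

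**Working it through.** **1. The plan's own power figure.** Inputs from the Aim 1 statistical section: 20 (SD 5) versus 26 (SD 4) AU, 15 per group, two-sided alpha 0.05. With SD 5 in both groups, power is 88.7% (t test) or 90.8% (normal approximation), so the stated 90% reproduces. With the planned controls it is 97% (15 vs 35, HM2) and 98% (15 vs 60, HM3).

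**2. The window.** Values in an inclusive 14-day window = floor(14/spacing) + 1. At 14-day spacing this is 2; at daily spacing it is 15. Three values span 2 × spacing: 28 days for outpatients, 2 days for inpatients. Three values within 14 days need spacing of 7 days or less.

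**3. Outpatient share of controls, literal reading.** Inputs: 32 months; 35% excluded; LLH in 30% (HM2) and 20% (HM3); 3 HM3 implants per month, and 2 HM2 per month by subtraction from 5 (an assumption, since the HM2 number is not printed).

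| | New-implant controls | Outpatient controls |
|---|---|---|
| HM2 | 64 × 0.65 × 0.70 = 29.1 | 95 × 0.65 × 0.70 = 43.2 |
| HM3 | 96 × 0.65 × 0.80 = 49.9 | 30 × 0.65 × 0.80 = 15.6 |

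- HM2: low (35 − 29.1)/35 = 17%; whole pool 43.2/(43.2 + 29.1) = 60%.
- HM3: low (60 − 49.9)/60 = 17%; high 15.6/60 = 26%.

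The low ends hold at 32 months. If recruitment ran longer and new implants were preferred, the shares could be lower.

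**4. What a setting gap would do.** The bias in the mean difference is share × gap. The documents give no gap, so 1 to 5 AU is an assumption with no source; the sign is unknown and zero is possible. Simulated Student t test, SD 5, 15 cases, 40,000 runs:

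| Controls (outpatients) | False-positive rate, gap 1 to 5 AU, no LLH effect | Power for a true 6 AU, opposite-sign gap 1 to 5 AU |
|---|---|---|
| HM2 35 (6) | 5% to 7% | 96% to 89% |
| HM2 35 (21) | 7% to 42% | 93% to 41% |
| HM3 60 (10) | 5% to 7% | 98% to 93% |
| HM3 60 (16) | 5% to 12% | 97% to 86% |

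The largest bias shown is 21/35 × 5 = 3 AU, half the planned effect.

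**5. Would the plan's screen catch it?** Suppose setting were added to the list but kept under the significance screen. Fisher tests of outpatients among cases versus controls give p = 0.16 (0/15 vs 6/35), p < 0.001 (0/15 vs 21/35), p = 0.20 (0/15 vs 10/60) and p = 0.03 (0/15 vs 16/60). At the low shares no adjustment would follow.

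**6. Accrual.** Cases from new implants alone by month 32: HM2 2 × 0.65 × 0.30 × 32 = 12.5; HM3 3 × 0.65 × 0.20 × 32 = 12.5. Fifteen would take about 38.5 months, within the 6-to-12-month extension that the plan allows. With 12 cases, power is 94% (vs 35) and 96% (vs 60).

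**7. Aim 2 unit.** 10 g/dL = 10,000 mg/dL, which is 1,000 times Aim 1's 10 mg/dL bound.

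**The case against.** **The literal reading may not be what is intended.** Outpatients are invited to research visits, 125 are counted toward the timeline, and the 30% and 20% LLH rates are applied to the whole durable sample. This stands, and it favors the relaxed reading. But it exchanges a possible confounding problem for an unwritten classification rule whose error cannot be computed. The figures in step 4 belong to the literal reading only.

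**Other routes to three values.** The background section calls LDH screening biweekly, which could mean twice a week, but the two Aim 1 passages say every 2 weeks. Unscheduled laboratory tests could fill the window, but the plan provides for none.

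**Continuous reanalysis.** The Aim 1 paragraph on anticipated results allows LLH to be reanalyzed as a continuous variable if no increase is seen. This is optional, covers only part of the risk of a missed effect, and does nothing about a false positive.

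**Stronger readings that the documents do not support.**
- A reader might infer that all HM2 controls could be outpatients, since the pool of 95 exceeds the screening target of 80. But new implants without LLH are sampled at discharge, and both groups are recruited until 15 cases are found. Finding 15 cases among new implants at 30% implies about 15/0.30 × 0.70 = 35 new-implant controls. Adding all 43 outpatients gives 43/78 = 55%, so the share tops out near 55% to 60%.
- Aim 2's recruitment section says "52 outpatients identified through our CF MCS patient registry on durable devices with LLH are available for screening". A reader might compare 52 with the number that Aim 1's rates predict and infer misclassification. Aim 2 uses a different definition, with LDH from 240 U/L and no upper limit, so the comparison shows nothing.

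**Aim 2.** The unit is probably a typing slip. The Benefits section links LDH and haptoglobin with an or, which hints at intent, but it omits free hemoglobin and is not an eligibility rule. The connector therefore remains open.

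**Conclusion.** The contradiction in Aim 1 is certain and rests on counting alone. It concerns HM2 and HM3 outpatients; VA ECMO and Impella patients have daily inpatient values and are not affected. Its consequence for the estimate is not determined by the documents. The literal-reading ranges (about 5% to 42% false positives for HM2, 5% to 12% for HM3) depend on the accrual assumptions in step 3 and on an unsourced gap, and the true bias may be zero. The stated power is sound, and the loss from fewer cases is minor. The issue is classification and confounding, not sample size.

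The Aim 2 defect is separate. It leaves eligibility unclear but does not bias the randomized comparison. Both should be fixed.

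**What to change.** **Aim 1 rule.** Reconcile the 14-day window with the 2-weekly outpatient schedule, and state the repeat rule for the no-LLH group on the same basis. The documents do not say whether Aim 1 has already enrolled. If it has, report the rule actually used in each setting and the case and control counts by setting.

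**Aim 1 analysis.** In the HM2 and HM3 comparisons, report an analysis adjusted for inpatient/outpatient status and time since implant, without the significance screen. If all cases come from one setting, report the within-setting comparison instead, because adjustment then only sets the outpatient controls aside.

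**Aim 2.** Reconcile the free-hemoglobin unit with Aim 1, and state the unit and the AND/OR connector actually applied to enrolled participants.

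**Cost.** Wording, plus two covariates from the medical record; no new samples. The covariates are likely to be correlated, with only 15 cases per device. If only new-implant controls inform the contrast, power for 6 AU (SD 5) is 95.8% (15 vs 29) or 87.5% (15 vs 14) for HM2, and 98.0% (15 vs 50) or 97.6% (15 vs 44) for HM3. If reconciliation lengthens the outpatient window, hemolysis has more time to change within it.
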